**Low Intensity Focused Ultrasound of Medial Temporal Lobe
Regions for the Improvement of Learning and Memory /
Low Intensity Focused Ultrasound as a Non-Invasive Neural
Prosthetic for the Improvement of Emotion Regulation**

NCT03717922
Document Date: 12/8/2023

APPROACH

Participants. Participants will consist of 21 adults aged 35-90

Subject Recruitment. Participants will be recruited from the Human Connectome Project – Aging participant pool and through fliers placed around campus and greater Los Angeles.

Eligibility. Inclusion criteria: 1) age 35-90, 2) right handed, 3) English dominant language.

Exclusion criteria: contraindications for MRI (e.g. metal implants, pregnancy), history of head injury sufficient to warrant medical attention, history of alcohol or substance abuse or dependence, history of major psychiatric illness requiring treatment, history of cancer or other neoplastic syndromes, history of major neurologic illness (e.g. epilepsy).

Procedures.

Crossover Design. This study will be conducted using a crossover design in which each participant will complete two visits spaced two weeks apart. At one visit, they will receive LIFUP sonication to the right amygdala, and at the other, they will receive sonication to the left entorhinal cortex. The order of conditions will be randomized and counterbalanced across participants. Participants will be blinded to condition order, and all other testing will be conducted the same at both visits.

Screening. Participants who have consented to be contacted regarding future research projects will be contacted by study staff who will conduct a telephone screening to ensure eligibility.

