fMRI and LIFUP administration. Prior to receiving LIFUP sonication, the LIFUP transducer will be aimed at the appropriate target region for the visit (either the amygdala or the entorhinal cortex) and gently strapped in place to their head. Participants will then return to the scanner where a T1 image will verify the position of the LIFUP transducer and allow for estimation of the spatial location of the sonication beam focus. If needed, adjustments to transducer placement will be made to ensure that the beam focus is correctly aimed; an additional T1 will be collected after adjustment. Once correct placement of the transducer has been confirmed, LIFUP will be administered in 10 sonifications at 650kHz, 720mW/cm, duty cycle 5% duration 30s, with 30s spacing between sonifications. LIFUP will be administered with a pulse repetition frequency of 10Hz for amygdala sonication and 100Hz for entorhinal cortex sonication. BOLD fMRI will be collected simultaneously during LIFUP administration.

MRI Data Acquisition. We will use a 3-Tesla Siemens PRISMA scanner. We will collect T1, T2, hi-res hippocampal T2, and diffusion-weighted structural images for each participant.

Additionally, we will collect arterial spin labeling and BOLD fMRI both before and after LIFUP, as well as BOLD fMRI during LIFUP administration. We will be using Human Connectome Project scan sequences to collect these images; detailed information about the protocols can be obtained here: <http://www.humanconnectome.org/documentation/Q1/imaging-protocols.html>.

Behavioral Testing. Participants will be administered the behavioral tests described below twice at each of their in-person sessions; once before LIFUP and once after LIFUP.

Verbal Free Recall Task. Verbal memory will be assessed using the Rey Auditory Verbal Learning Test (RAVLT) which involves repeated presentation of a list of 15 words. The order of RAVLT form administration will be randomized and counterbalanced across participants.

Spatial Navigation Memory Task. Participants will be presented with a computerized spatial arena simulating a museum art gallery. They will be instructed to learn the locations of three objects placed throughout the gallery. After the Learning Phase, the subjects will then be asked to locate the objects' shown location sans stimuli immediately after learning the set of locations of each object. After each learning phase, participants will complete an unrelated Distractor Task

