within the task but unrelated to the Mission. The navigation and distractor task paradigm will be repeated three times. During the fourth and final trial, retrieval of spatial information during this trial will be measured as the distance between the location that participants selected and the true location of the object. Shorter distances will indicate better spatial memory performance. This assessment has four forms, the order of which will be randomized and counterbalanced across participants.

Brief Visuospatial Memory Test. In this test, the participant is presented with a 2x3 array of geometric figures for 10 seconds, then instructed to draw the figures from memory in the correct location on the page. The task consists of three learning trials, one long delayed recall trial, and one recognition trial. Learning performance will be calculated as the proportion of presented figures and figure locations successfully recalled during the initial presentations of the six-figure array. Long delayed recall memory performance will be calculated as the proportion of presented figures and figure locations successfully recalled freely after a 20-minute delay. Memory retention will be calculated as the proportion of presented figures successfully identified during a forced-choice recognition task. This assessment has 4 forms that will be used for repeat testing, the order of which will be randomized and counterbalanced across participants.

State Trait Anxiety Inventory. This is a questionnaire used to measure anxiety-like symptoms. The first half of the questionnaire asks about the degree to which several listed statements align with how a participant feel at the current moment (state anxiety). The second half asks about the degree to which the listed statements align with how a participant typically feels (trait anxiety).

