Physiological Analysis. To determine the effect of LIFUP on psychophysiological reactivity to emotionally-salient stimuli, interbeat intervals (IBIs) will be calculated for each stimulus presentation using Autonomic Nervous System Laboratory (ANSLab). These IBIs in response to stimuli will be analyzed using multilevel modeling with a repeated measures within-subjects design, with target (amygdala / entorhinal cortex), timepoint (pre / post LIFUP), and instructions (view, watch, reappraise) included as model factors.

Hypothesis 3. LIFUP of the entorhinal cortex will result in better performance on memory tasks compared to both amygdala LIFUP and pre-LIFUP conditions.

Behavioral Analysis. To determine the effect of LIFUP stimulation on memory performance, performance on memory assessments before LIFUP, after entorhinal cortex LIFUP, and after amygdala LIFUP will be compared using ANOVA.

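### The Hypothesis 3 ANOVA names no visit term, so the entorhinal-versus-amygdala memory contrast can lose power if scores differ between visits; a visit term is nearly free but does not repair entorhinal versus pre-LIFUP

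*Combined protocol and SAP*

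**What the plan says.** The Hypothesis 3 analysis is one sentence in the combined protocol and SAP (Hypothesis 3, Behavioral Analysis): "performance on memory assessments before LIFUP, after entorhinal cortex LIFUP, and after amygdala LIFUP will be compared using ANOVA". The hypothesis has two parts: "LIFUP of the entorhinal cortex will result in better performance on memory tasks compared to both amygdala LIFUP and pre-LIFUP conditions".

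Under Crossover Design, at one visit "they will receive LIFUP sonication to the right amygdala, and at the other, they will receive sonication to the left entorhinal cortex". On allocation: "The order of conditions will be randomized and counterbalanced across participants". Under Behavioral Testing: "Participants will be administered the behavioral tests described below twice at each of their in-person sessions; once before LIFUP and once after LIFUP". Each memory test is therefore given four times, and within a visit the pre-LIFUP test always comes first.

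Forms are handled by design. For the spatial navigation task: "This assessment has four forms, the order of which will be randomized and counterbalanced across participants". The Brief Visuospatial Memory Test also has four counterbalanced forms. For the RAVLT, "The order of RAVLT form administration will be randomized and counterbalanced across participants", but the number of forms is not given.

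The Hypothesis 3 sentence names no visit, form or participant term. By contrast, the interbeat-interval data in the Physiological Analysis are to be "analyzed using multilevel modeling with a repeated measures within-subjects design", with the factors listed.

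**The concern.** A participant's post-entorhinal and post-amygdala scores are two weeks apart, at different visits. If scores shift between visits, the shift adds to the difference in one order group and subtracts from it in the other. Balance between the orders removes nearly all of it from the mean. It does not remove it from the estimated variance unless visit is in the model. The standard error is then too large, and with 21 participants there is little power to spare.

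The second part of the hypothesis, entorhinal versus pre-LIFUP, has a different problem. Post always follows pre within a visit, so a practice gain looks the same as a LIFUP effect. A reader who adds a visit or form term might think that this has been dealt with. It has not.

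**Working it through.** **Inputs.** From the documents: 21 participants (11/10 by order at best), two visits, four administrations of each test. The documents give no power, alpha, effect size, SD, visit effect, form effect or practice gain for Hypothesis 3, so there is no plan figure to reproduce. Assumed: two-sided 5%, effect δ = 0.65, no dropout, participant in the model. The unit throughout is the SD of the within-person post-versus-post difference, so the session residual variance is 0.5. Visit shift d is the mean change from visit 1 to visit 2.

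**1. Paired comparison, entorhinal versus amygdala.** Model: Dᵢ = δ + sᵢd + eᵢ, with eᵢ ~ N(0,1) and sᵢ = +1 or −1 by order.

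- Without visit, the mean estimates δ ± d/21. Its true SE is 1/√21 = 0.218. The expected sample variance is 1 + d²(21 − 1/21)/20 = 1 + 1.048d². At d = 0.5 this is 1.262, so the SE used is about 1.123/√21 = 0.245.
- With visit, the estimate is the average of the two order-group means. SE = ½√(1/11 + 1/10) = 0.2185, noncentrality 0.65/0.2185 = 2.975, 19 df, power 80.6% at any d.
- Without visit at d = 0, noncentrality is 0.65√21 = 2.979, 20 df, power 80.9%.

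For d > 0 the residual sum of squares is noncentral chi-square (noncentrality 20.95d²). The ranges show which order has 11 people:

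| d | Power without visit | Power with visit | Type I error without visit |
|---|---|---|---|
| 0 | 81% | 80.6% | 5.0% |
| 0.25 | 77-81% | 80.6% | 4.4% |
| 0.5 | 70-77% | 80.6% | 3.0% |
| 0.75 | 58-69% | 80.6% | 1.6% |
| 1.0 | 43-59% | 80.6% | 0.7% |

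**2. Four-session model** (participant, and condition as pre, post-entorhinal, post-amygdala; 84 scores; 84 − 21 − 2 = 61 df). At d = 0.5 the omitted visit effect adds about 21 × 4 × 0.25² = 5.25 to the residual sum of squares, or 5.25/61 = 0.086 on a variance of 0.5. That is 17% inflation, against 26% in the paired case. Power is 76-82% without visit and 83-84% with it.

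**3. Form, in the four-session model with visit.** With four equally spaced form effects of SD 0 / 0.25 / 0.5:

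- Forms counterbalanced within order: power without form 84 / 79 / 64%, with form 83-84%.
- Form order only random: power without form 84 / 77 / 64%, with form 81%.

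The size of the loss depends on the form layout; another layout gave 74% without form at SD 0.5. If only the post scores are modelled, adding visit and form when neither has an effect takes power from 79.4% to 72.1% (effect 0.643), and nearly all of that loss is due to form.

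**4. Entorhinal versus pre-LIFUP, no LIFUP effect.** With both pre scores in the model, SE = √(0.5 × 1.5/21) = 0.189. A post-over-pre gain of 0.25 gives noncentrality 0.25/0.189 = 1.32 and a rejection rate of 26% without visit and form; with both it is 25%. Gains of 0.1 and 0.5 give 8% and 74% either way. The three-level F test rejects 8 / 27 / 81% at gains of 0.1 / 0.25 / 0.5, while entorhinal versus amygdala stays at 5%. Adding position within visit to the model with visit does not help: the design matrix has 25 columns and rank 24, so practice and pre-to-post change cannot be separated.

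**The case against.** The strongest reply is that the design already deals with visit and form. Both orders are randomised and counterbalanced, the contrast is valid as planned, and what remains is precision that depends on an effect the documents never quantify. With no visit effect nothing is lost. The large losses come from the paired analysis at shifts that no passage supports; if all four sessions are analysed, the loss is modest. All of this stands, and it limits the point to a conditional one.

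A second reply is that one sentence saying only ANOVA is being read selectively: participant is assumed present although it is not named, while visit is taken as absent. Leaving participant out would cost more (57% instead of 83% with no visit effect, if participant variance equals session variance). That is fair, and it is why the fix also asks for the within-participant statement. The crossover design makes a within-participant analysis the natural reading, so the documents do not support a charge that participant will be omitted.

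A reader might infer that the missing term biases entorhinal versus amygdala or produces false positives there. It does not: the 11/10 split leaves at most d/21, and in the paired comparison type I error is at or below 5%. Nor do the documents support saying that power will be lost; that needs a real visit or form effect.

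Finally, Hypothesis 3 asks for superiority over both comparators. If both contrasts must succeed, the joint error under practice alone is bounded by the entorhinal-versus-amygdala test, near 5%. The plan does not state such a rule, so the exposure in section 4 of the working applies if the pre-LIFUP contrast or the F test is read alone.

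**Conclusion.** The point holds in conditional form. The planned ANOVA leaves out a visit term that the crossover provides for. For entorhinal versus amygdala this can cost power but does not create material bias. At an assumed visit shift of 0.5 the loss is about 4 to 11 points in a paired comparison and about 1 to 8 points in a four-session one. At zero shift there is no loss. These sizes rest on the assumed effect of 0.65, two-sided 5%, no dropout and a within-participant analysis.

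Visit is the firm recommendation. Form is optional, because its benefit depends on unstated form differences and on the layout. Neither term repairs entorhinal versus pre-LIFUP.

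There is also a limit on interpretation. With no sham visit, entorhinal versus amygdala shows a difference between targets. By itself it cannot tell entorhinal improvement from amygdala impairment.

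Label: cheap improvement.

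**What to change.** Reword the Hypothesis 3 analysis to state that the comparison is within participant and that visit is a fixed factor. The simplest version is the post-entorhinal minus post-amygdala difference for each memory score, adjusted for visit order. It uses one degree of freedom and costs about 0.3 points of power if visits do not differ (80.9% to 80.6%). Do not add form to this post-only comparison.

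If all four sessions are modelled instead, state that both pre-LIFUP scores enter. Form may then be added for the two four-form tests. It uses three degrees of freedom, costs 0 to about 2 points if the forms are equal, and recovers power if they differ. In that model, scores from the same visit may be correlated. With 25% or 50% of session variance shared within a visit, a participant-only model has type I error of 6.0% or 7.3% for entorhinal versus amygdala. A participant-by-visit intercept brings this to about 5.8% at both. The paired version with visit stays at about 5%.

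State also that a claim of entorhinal benefit requires entorhinal versus amygdala to succeed, and that neither entorhinal versus pre-LIFUP nor the three-level F test will be taken alone as evidence of a LIFUP effect. These are changes to SAP wording only; no new data are needed.

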motion artifacts (using framewise displacement calculations, DVARS and within-subject independent component analysis), scrubbing, slice timing, unwarping and spatial smoothing (Gaussian Kernel FWHM = 8mm). Functional data will be linearly registered to stereotaxic MNI space and co-registered with anatomic data for each participant. Processing of diffusion imaging will include correction for motion, eddy distortion and susceptibility induced distortion and then fitting diffusion tensors to the data, Subjects with greater than 3mm mean displacement will be excluded from analyses. Structural data (T1 and DTI) will be linearly registered to the standard MNI152 T1 2mm brain.

Stimulation-related fMRI Analysis. BOLD fMRI will be collected continuously during the LIFUP paradigms. A block-design model will be used to statistically compare the BOLD signal during LIFUP stimulation blocks to the BOLD signal during no-stimulation blocks. To examine effect of stimulation to target ROI activity, we will extract average BOLD response rates in both the targeted and control (non-targeted) region for each of the blocks and use mixed-effect models to compare activity during LIFUP conditions (on / off) within each ROI. To examine LIFUP-related network connectivity, we will use a seed-based approach and examine whole brain connectivity with the LIFUP target of interest and compare between stimulation (on-off) conditions using psychophysiological interaction modeling (PPI). To assess changes in connectivity in relationship to LIFUP, we will use dynamic connectivity to evaluate changes in ROI across each LIFUP condition. Finally, dynamic causal modeling will allow us to assess and compare how changes in activation in the LIFUP target may causally affect activation in other regions (e.g. increased amygdala activation leads to increased DLPFC activity).

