RS-fMRI. We will compare the functional connectivity of the brain at rest before and after stimulation. Independent component analyses (ICA) will be used to statistically extract functional networks from each participant's rs-fMRI. Dual-regression analysis will then compare resting state networks between baseline and post-LIFUP to determine the effect of LIFUP on resting state functional connectivity. Age, sex and education will be included as additional regressors. Dual regression will also assess the association between these LIFUP-related longitudinal resting state network changes and emotional reactivity and memory performance.

Arterial Spin Labeling. Pulsed Arterial Spin Labeling (PASL) scans produce a perfusion image with voxel values representing local perfusion rates. For each subject, will be collected both before and after LIFUP. These PASL images will then be linearly registered to each subject's T1 structural image. Perfusion images will be processed by using the BASIL (Chappell et al., 2008) toolbox, including partial volume correction, then transferred to MNI space using non-linear registration in FSL. Then, a comparison of pre-vs-post tFUS sonication perfusion in the amygdala and entorhinal cortex will be conducted individually for each subject by subtracting the registered pre- sonication perfusion map from the post-sonication perfusion map. A 2×2 repeated measures analysis of variance (ANOVA), corrected for multiple comparisons using False Discovery Rate (FDR), will then be used to compare the longitudinal perfusion changes between amygdala sonication and ErC sonication.

Hypothesis 2. LIFUP of the amygdala will result in reduced subjective emotional reactivity to emotionally-salient stimuli compared to those presented before LIFUP; this reduction will not be observed with entorhinal cortex LIFUP.

Behavioral Analysis. Subjects, who will be unaware of the exact timing of the sonication onset, will be asked to report any unusual feelings, sensations or distress. To determine the effect of LIFUP on emotional reactivity, analyses of variance (ANOVA) will compare subjective valence

and arousal ratings between pre-LIFUP and post-LIFUP administrations of the IAPS task. Additionally, state and trait anxiety scores will be compared pre and post-LIFUP to determine LIFUP-related changes in anxiety levels.

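### Perfusion and memory are planned as ANOVAs that, in complete-case form, discard participants who miss visit 2; a mixed model, as already named for ROI BOLD and interbeat intervals, would use their visit-1 data at little cost

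*Combined protocol and SAP*

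**What the plan says.** All references are to the combined protocol and SAP.

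- **Participants and Crossover Design.** "Participants will consist of 21 adults aged 35-90", and "each participant will complete two visits spaced two weeks apart", one target per visit. "The order of conditions will be randomized and counterbalanced across participants". Behavioral Testing adds that the tests are given before and after sonication at each visit.
- **Arterial Spin Labeling.** Perfusion change is compared between the two sonication targets by "A 2×2 repeated measures analysis of variance (ANOVA), corrected for multiple comparisons using False Discovery Rate (FDR").
- **Hypothesis 2, Behavioral Analysis.** "analyses of variance (ANOVA) will compare subjective valence" and arousal before and after sonication. No repeated-measures form is stated and no target factor is named. Anxiety scores are to be compared before and after, with no method named.
- **Hypothesis 3, Behavioral Analysis.** "performance on memory assessments before LIFUP, after entorhinal cortex LIFUP, and after amygdala LIFUP will be compared using ANOVA". Again the repeated-measures form is not stated.
- **Stimulation-related fMRI Analysis.** For ROI BOLD the plan will "use mixed-effect models to compare activity during LIFUP conditions (on / off) within each ROI".
- **Physiological Analysis.** Interbeat intervals "will be analyzed using multilevel modeling with a repeated measures within-subjects design", with target, timepoint and instruction as factors.

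No section covers a missed second visit, missing data, replacement or the analysis population. The only analysis exclusion stated is the 3 mm mean-displacement rule for imaging.

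**The concern.** A participant who attends only visit 1 still supplies a complete before/after pair for one target. A classical repeated-measures ANOVA needs every cell filled, so it discards that pair whenever target is a within-subject factor. A mixed model need not.

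The named methods could therefore treat the same participant differently from one outcome to the next. Within Hypothesis 1, BOLD could rest on more people than perfusion. On the picture task, interbeat intervals could rest on more people than the ratings of the same images. Precision is lost as well. If the chance of returning depends on how visit 1 went, a completers-only before/after change is also biased. The plan names no rule that would prevent this, although it already uses the better-suited model class for two outcomes.

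**Working it through.** **Which analyses are exposed.**

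| Outcome | Method named | One-visit participant |
|---|---|---|
| Perfusion | 2×2 repeated-measures ANOVA comparing targets | Dropped in complete-case form |
| Memory | ANOVA including both post-sonication conditions | Dropped if run as a classical within-subject ANOVA |
| Ratings | ANOVA, only before/after named | Kept if run separately by target; dropped if target is a within-subject factor |
| Anxiety | None named | Undetermined |
| ROI BOLD, interbeat intervals | Mixed or multilevel model | Can be kept; no inclusion rule is stated |

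**Inputs.** From the plan: 21 participants, two visits, counterbalanced order (11:10 at best). The plan gives no dropout rate, SD or correlation, so the rest are assumptions: change scores with SD 1, and correlation ρ between the two visits' change scores of 0, 0.3 or 0.5. No figure in the plan bears on dropout, so there is none to reproduce.

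**Precision.** Assume 17 complete pairs plus two one-visit participants per target (17 + 4 = 21). Generalised least squares on all visits, relative to pairs only, gives these variance ratios:

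- Target contrast: 17 / (17 + 2(1−ρ))
- Within-target change: ½[(1−ρ)·17/(17 + 2(1−ρ)) + (1+ρ)·17/(17 + 2(1+ρ))]

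| ρ | Contrast ratio | Within-target ratio |
|---|---|---|
| 0 | 17/19 = 0.895 | 0.895 |
| 0.3 | 17/18.4 = 0.924 | 0.887 |
| 0.5 | 17/18 = 0.944 | 0.874 |

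Variance falls by 6-11% for the contrast and 11-13% for the within-target change. Since √0.944 = 0.972 and √0.874 = 0.935, standard errors fall by about 3-7%.

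**Bias in the before/after change.** Assume no true effect and a logistic chance of missing visit 2, with intercept −1.65 and slope 1 per SD of worsening at visit 1. This gives 20% dropout. The mean visit-1 change among those who return is then −0.173 SD. The visit-2 change carries ρ times that, so the average over visits is −0.173(1+ρ)/2:

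- ρ = 0: −0.087
- ρ = 0.3: −0.113
- ρ = 0.5: −0.130

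**Bias in the amygdala-minus-entorhinal contrast.** Under the same model the contrast is shifted by −0.173(1−ρ) in the 11 amygdala-first participants and by +0.173(1−ρ) in the 10 entorhinal-first. The net is −0.173(1−ρ)/21: −0.008, −0.006 and −0.004 SD for the three values of ρ. Counterbalancing cancels almost all of it.

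**Range over dropout rate and mechanism.** A second simulation used unit-SD scores with correlation 0.5 or 0.7, 2/21 or 4/21 missing visit 2, and no true effect:

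| Withdrawal mechanism | Completers-only amygdala before/after | Completers-only target-by-time contrast |
|---|---|---|
| Completely at random | about 0 | about 0 |
| Depends on visit-1 post score, both orders | −0.03 to −0.08 | under 0.01 in size |
| Same, amygdala-first order only | −0.04 to −0.11 | −0.04 to −0.11 |

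A likelihood-type mixed model on all observed visits stayed within 0.004 SD of zero throughout. A before/after analysis run separately by target on all attended visits also stayed close to zero.

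**The case against.** The strongest reply is that the plan does not prescribe the deletion. Only perfusion is stated to be repeated-measures. Ratings and memory say ANOVA without a form, and a before/after ratings analysis run by target would keep a one-visit participant. Nor does the plan state an inclusion rule for ROI BOLD or interbeat intervals, so the difference in analysed populations is inferred on both sides. The 3 mm motion rule could make the imaging sets differ under any model. All of this stands and limits the point. It does not clear perfusion, or memory if run as a classical within-subject ANOVA. For ratings, Hypothesis 2 also expects no reduction with entorhinal sonication, and testing that calls for target as a factor.

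The second reply is size. A bias of 0.09 to 0.13 SD is roughly half the standard error of a mean change at 17 participants (1/√17 = 0.24 SD), and the precision gain is modest. That is correct.

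A reader might go further and infer that withdrawals would bias the tests of Hypotheses 2 and 3. The documents do not support that. If dropout works alike in both orders, both targets shift together. A spurious fall after amygdala sonication would then appear after entorhinal sonication too, and would not favour the specificity that Hypothesis 2 claims. The mechanism considered, worsening at visit 1 discouraging return, has no shown link to memory scores. Nothing in the plan suggests that dropout would differ by order.

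**Conclusion.** The point holds as an inexpensive improvement to the analysis, not as a demonstrated bias in the hypothesis tests. Perfusion and memory are exposed to loss of usable visit-1 data under complete-case ANOVA; ratings are exposed only if target enters as a within-subject factor.

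With 17 of 21 completing both visits, the avoidable loss is about 6-13% of variance. With 20% outcome-dependent dropout, the completers-only before/after change is off by about −0.09 to −0.13 SD. The between-target contrast is off by less than 0.01 SD unless dropout differs by order. There is no bias if dropout is completely at random, and no bias is shown for Hypothesis 3. All these sizes rest on assumed dropout rates, mechanisms and correlations. If everyone attends both visits with complete data, the issue does not arise.

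**What to change.** Analyse perfusion change, valence and arousal ratings, and memory scores with linear mixed models fitted by REML: target, timepoint where applicable, period/order, a participant random effect, and a small-sample degrees-of-freedom method. Use the same model for anxiety scores. The period term matters because one-visit data would normally all come from visit 1; without it, practice or period effects could enter the target contrast when withdrawals are unequal by order. Keep the planned FDR correction for perfusion.

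State that every participant with at least one completed before/after visit is included, both for these outcomes and for ROI BOLD and interbeat intervals. Show the complete-pairs analysis as a sensitivity analysis, and report one-visit participants by first target and reason.

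The cost is plan wording and minor programming, with no new data. The downside is reliance on missing at random (dropout depending only on observed data) and on a degrees-of-freedom approximation at n = 21.
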